3.1 Study Design

This is an open-label, multi-center Phase 2 study in patients with advanced solid tumors, including *RET* fusion-positive solid tumors (e.g., NSCLC, thyroid, pancreas, colorectal), *RET*-mutant MTC, and other tumors with *RET* activation (e.g., mutations in other tumor types or other evidence of *RET* activation).

Patients with *RET* alterations in tumor and/or blood will be identified through molecular assays. The *RET* alteration results should be generated from a laboratory with certification by China National Accreditation Service for Conformity Assessment (CNAS), External Quality Assessment (EQA), Clinical Laboratory Improvement Amendments (CLIA), College Of American Pathologists (CAP) or other similar certification. The Sponsor should be contacted to discuss test results to ensure trial eligibility.

The Schedule of Assessments (refer to [Table 7-1](#)) consists of a screening period, a treatment period including an End of Treatment (EOT) visit, a Safety Follow-up (SFU) visit, and Long-term Follow-up (LTFU). Ongoing safety, and disease assessments (for patients without PD), disease status, survival, and subsequent anticancer therapy(ies) will be assessed during LTFU.

Selpercatinib will be administered in oral form BID. Dosing will be fixed as total milligram (mg; as opposed to weight-based or body surface area [BSA]-based).

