3.3 General Treatment Procedures

Patients will receive 160 mg BID selpercatinib on Cycle (C) 1 Day (D) 1 in accordance with the cohort assignment. Cycles are measured in 28-day increments.

Individual patients will continue daily selpercatinib dosing until PD, unacceptable toxicity, or other reasons for treatment discontinuation, as outlined in Section 6.4. Twenty-eight days after the last dose of study drug (+7 days), all treated patients will undergo an SFU visit. Patients with documented PD may be allowed to continue selpercatinib if the patient is tolerating treatment and, in the opinion of the Investigator, the patient is deriving clinical benefit from continuing study treatment, and continuation of treatment is approved by the Sponsor.

After treatment discontinuation, all patients will enter the LTFU part of the study until death, withdrawal of consent, lost to follow-up or the Sponsor makes a decision to close the study. LTFU will include follow up for survival status, which may be conducted by telephone. During LTFU, for practical reasons and to minimize patient inconvenience, continued disease assessments by imaging until disease progression are optional. For any patient who is lost to follow-up, the study site will attempt to ascertain survival information via public database search. If survival status still cannot be ascertained, patients will be considered lost to follow-up and will be censored appropriately.

[figure not shown]

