6.3 Concomitant Medications

6.3.1 General

All medications that were used from the time that written informed consent has been obtained through the SFU visit (at least 28 days [± 7 days] after the last dose of study drug) will be recorded in the eCRF. These are to include prescription and nonprescription medications, transfusions, vitamins, and nutritional supplements, and other remedies. Additional prior excluded medications are indicated in the Exclusion Criteria (Section 4.2).

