| Confirmatory disease assessment ^z | | | | | | At least 4 weeks post 1 st PR | | | |
| Blood sample for intensive PK ^{aa} | | X | X | | | | | | |
| Blood sample for PopPK ^{bb} | | X | | | | D1 of each cycle Predose sample to be drawn | | | |
| EORTC QLQ-C30 ^{cc} | | X | | | | Every 8 weeks (±7 days) starting with D1 C3 through D1 C13. Every 12 weeks (±7 days) thereafter | X | | |

| Visit Window | Screening | Cycle 1 | | | | Cycle 2-higher | SFU ^b | | LTFU ^c |
|--|-----------------------------------|---------------|---------------|----------------|-----------------------------|----------------------|------------------------------|-----------------|-------------------|
| | Up to 28 days prior to first dose | D1 ±2 Days | D8 ±2 Days | D15 ±2 Days | D22 ^d ±2 Days | ±2 Days | EOT ^a ≤ 7 days | D 28 ±7 days | |
| Dispense selpercatinib | | X | | | | D1 of each cycle | | | |
| Selpercatinib administration | | | | | | | | | |
| Patient dosing diary | | | | | | | | | |
| Patient bowel diary (MTC only) ^{dd} | | X | X | X | X | D1 C2, 3, 4, 5, etc. | X | | |
| Adverse events ^{ee} | | | | | | | | | |
| Concomitant medications ^{ff} | | | | | | | | | |
| Survival ^{gg} | | | | | | | | X | X |

Abbreviations (for Table 7-1 and Footnotes): ACTH-adrenocorticotrophic hormone; AE-adverse event; ALP-alkaline phosphatase; ALT-alanine aminotransferase; AST-aspartate aminotransferase; BUN blood urea nitrogen; C-cycle; CEA carcinoembryonic antigen; CR complete response; CT-computed tomography; D-day; ECG electrocardiogram; ECOG-Eastern Cooperative Oncology Group; EORTC QLQ-C30-European Organization for Research and Treatment of Cancer Quality of Life Questionnaire-Core 30; EOT-End of Treatment; IV intravenous; LDH lactate dehydrogenase; LTFU long-term follow up; MTC medullary thyroid cancer; MRI magnetic resonance imaging; PD-progressive disease; PK pharmacokinetics; PR partial response; RBC-red blood cell; SAE-serious adverse event; SFU safety follow-up; TSH-thyroid-stimulating hormone; T3-free triiodothyronine; T4-free thyroxine; WBC white blood cell.

- End of Treatment (EOT): +7 days of the last dose or the decision to terminate treatment. If lab testing is performed ≤7 days prior to EOT, repeat testing does not need to occur on EOT.
- Safety Follow-Up (SFU): 28 days (±7 days) after last dose of study drug.
- Long-Term Follow-Up (LTFU): approximately every 3 months (±1 month) for up to two years after the last dose of study drug.
- Telephone contact for safety.

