- x. If not performed within the last 8 weeks.
- y. Patients who discontinue study drug for reasons other than PD (e.g., AE, noncompliance, etc.) may (but for practical reasons and to minimize patient inconvenience, are not required to) undergo additional disease assessment by imaging (as specified above until PD, withdrawal of consent or initiation of a new anticancer therapy(ies)).
- z. Confirmatory scans: Minimum of 4 weeks (e.g., 28 days) after the first tumor evaluation showing a CR or PR by RECIST 1.1, if permitted by regulatory authorities. The next scan should continue according to the schedule above.
- aa. For 12 subjects in intensive PK testing, PK test performed on C1D1: Up to pre-dose, and post-dose 1 hour (± 15 minutes), 2 hours (± 15 minutes), and 4 hours (± 15 minutes), 8 hours (± 30 minutes) and 12 hours (± 30 minutes), C1D8: Up to pre-dose, and post-dose 1 hour (± 15 minutes), 2 hours (± 15 minutes), and 4 hours (± 15 minutes) and 8 hours (± 30 minutes).
- bb. For all enrolled subjects in PopPK testing, PK test performed on each cycle D1 predose.

- cc. EORTC QLQ-C30. The questionnaires should be answered by the subject to the best of his/her ability, prior to receiving drug on C1D1 and preferably prior to learning the results of the radiologic disease assessment for subsequent cycles.
- dd. Only for patients with a diagnosis of MTC and diarrhea at baseline. Two patient bowel diary cards will be dispensed on C1D15. The questionnaires should be answered by the subject to the best of his/her ability.
- ee. AEs and SAEs should be recorded from the time that written informed consent has been obtained through the SFU Visit.
- ff. Concomitant, ongoing medication(s) plus those administered within 14 days prior to the planned start of treatment.
- gg. Patients will be followed for survival status, date of progression, and subsequent anticancer therapy(ies) by telephone or other method.

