7.5 Safety Follow-up Visit (SFU)

Twenty-eight (28) days (+7 days) after the final dose of study drug (may be performed as part of the EOT visit if the latter was performed at least 28 days after final dose of the last cycle), the following will be performed:

- Symptom-directed physical examination, weight, and ECOG.

- Vital signs.
- Resting 12-lead ECG: only if prior ECG reading showed treatment-emergent abnormalities.
- Hematology.
- Serum chemistries.
- Urinalysis.
- Status of unresolved SAEs (if unresolved SAEs exist at the time of this visit, subsequent assessment for resolution may be conducted by phone if patient is not able to return to clinic).
- AEs.
- Concomitant medications.

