6.11.2. Adverse Event

The reported AE term will be coded using the latest version of the Medical Dictionary for Regulatory Activities (MedDRA). AE verbatim text will be mapped by the sponsor or designee to corresponding terminology within MedDRA, and the resulting System Organ Class (SOC) and Preferred Term (PT) will be used for AE summary. The severity of each AE will be graded by the Investigator based on version 5 of the National Cancer Institute (NCI) Common Terminology Criteria for Adverse Events (CTCAE). For AEs without matching terminology within the NCI-CTCAE, Version 5, the investigator will be responsible for selecting the appropriate SOC and assessing severity grade based on the intensity of the event. The causal relationship between the occurrence of an AE and study drug will be judged by the Investigator, and reported by answering yes/no in CRF.

Consolidated AE: Consolidated terms comprising clinically synonymous MedDRA preferred terms have been defined in order to assist in identifying relevant safety differences between treatment arms. Summaries of the incidence of these consolidated terms will supplement the summaries by MedDRA PTs specified in this section. The MedDRA PTs that are grouped under each of the consolidated terms will be provided in compound-level safety document.

A **serious adverse event (SAE)** is any AE during this study that results in one of the following outcomes:

- death
- initial or prolonged inpatient hospitalization (except for study drug administration)
- a life-threatening experience (that is, immediate risk of dying)
- persistent or significant disability/incapacity
- congenital anomaly/birth defect
- considered significant by the investigator for any other reason.

An AE will be regarded as **treatment-emergent**, if

- Its onset date occurs any time on or after the date of first dose up to 28 days after the last dose (or up to any time if serious and considered related to study treatment); or
- It occurs prior to first dose date and worsens while on therapy or up to 28 days after the last

dose of study treatment (or up to any time if serious and considered related to study treatment)

AEs will be summarized based on the number and percentage of patients experiencing events by MedDRA SOC and PT. If a patient experiences repeat episodes of the same AE (as defined by the MedDRA SOC and PT), the patient will only be counted once on the most severe CTCAE grade and the closest relationship to treatment.

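### The safety follow-up visit is 28 ±7 days in Table 7-1 but 28 +7 days in Sections 3.3 and 7.5, so AE recording may close up to 7 days before the SAP's 28-day TEAE window ends

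*Protocol*

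**What the plan says.** The current protocol text gives the window for the safety follow-up (SFU) visit in several places.

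- **Table 7-1.** The SFU column header gives day 28 ±7 days, and note b repeats it: "Safety Follow-Up (SFU): 28 days (±7 days) after last dose of study drug".
- **Section 3.3:** "Twenty-eight days after the last dose of study drug (+7 days), all treated patients will undergo an SFU visit".
- **Section 7.5:** "Twenty-eight (28) days (+7 days) after the final dose of study drug". The end-of-treatment visit may stand in for the SFU only "if the latter was performed at least 28 days after final dose of the last cycle".
- **Section 6.3.1** (concomitant medications) places the visit "at least 28 days [± 7 days"], a lower limit of 28 days combined with a tolerance that goes below it.

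Two further statements give the visit date its weight.

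- **Table 7-1 note ee:** "AEs and SAEs should be recorded from the time that written informed consent has been obtained through the SFU Visit".
- **SAP Section 6.11.2** treats an AE as treatment-emergent if it starts on or after the first dose and "up to 28 days after the last dose (or up to any time if serious and considered related to study treatment").

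**The concern.** The SFU visit fixes the point at which note ee stops AE recording. If it may fall before day 28, the period in which events are collected can be shorter than the period over which the SAP counts them. Two sites following different parts of the same protocol could then record different events for otherwise identical patients. The events at risk are new non-serious AEs and SAEs judged unrelated, with onset after an early SFU and no later than day 28. TEAE frequency and severity are a secondary endpoint (Section 9.1.2). The two windows also leave it unclear whether a day-21 visit is a protocol deviation.

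**Working it through.** No figure in the plan needs reproducing. The check is day arithmetic on the stated windows, with days counted from the last dose.

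**Windows**

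- Table 7-1 (header and note b): 28 − 7 = day 21 to 28 + 7 = day 35, which is 35 − 21 + 1 = 15 calendar days.
- Sections 3.3 and 7.5: day 28 to 28 + 7 = day 35, which is 35 − 28 + 1 = 8 calendar days.
- SAP Section 6.11.2: the counting window closes on day 28, except for serious related events, which have no limit.

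**Gap between the SFU and the end of the SAP window** = 28 − SFU day, or 0 if the visit is on day 28 or later.

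| SFU held on | Gap (days) |
|---|---|
| day 21 | 28 − 21 = 7 |
| day 24 | 28 − 24 = 4 |
| day 27 | 28 − 27 = 1 |
| day 28 to 35 | 0 |

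Under Table 7-1 the largest gap is 7 days (days 22 to 28). Under Sections 3.3 and 7.5 it is 0.

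**Is the sign a text-extraction slip?** Probably not. Each form appears in two separate places. Within the Table 7-1 notes, note a (end of treatment) carries a plain + and note b, next to it, carries ±.

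**Would events in the gap be captured anyway?** The text points both ways.

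- *For capture:* Section 3.1 states "Ongoing safety, and disease assessments (for patients without PD), disease status, survival, and subsequent anticancer therapy(ies) will be assessed during LTFU". Section 8.2.3 requires AEs after consent to be recorded and gives no end date.
- *Against capture:* note ee stops at the SFU. Section 7.6 names only later anticancer therapy and survival as possible long-term follow-up assessments, about every 3 months and possibly by phone.

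**Exposure at day 21.** Section 6.3.2 equates 5 half-lives with about 2 to 3 days, so one half-life is 2/5 = 0.4 to 3/5 = 0.6 days. By day 21, 21/0.6 = 35 to 21/0.4 = 52.5 half-lives have passed. If onset follows exposure, few new drug-caused events would start in the gap. The documents do not state that it does.

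**The case against.** The strongest reply is that the windows are nested. A visit on days 28 to 35 satisfies every passage, and a day-21 visit breaches Sections 3.3 and 7.5. Section 7 describes Table 7-1 as a summary that its subsections expand, and Section 7.5 has its own 28-day floor for a combined visit. Section 8 requires adherence to the study design including the schedule, but does not rank the schedule above the body text. On this reading the floor is day 28 and the table holds an uncorrected symbol. This is good evidence of intent and supports the direction of the fix. It does not remove the conflict: a coordinator scheduling from Table 7-1 is told that day 21 is acceptable.

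The second reply is that lost recording is inferred. Section 8.2.3.1 relieves investigators of actively seeking AEs only once study participation has ended, and a patient in long-term follow-up is arguably still participating. That makes later capture possible but does not assure it, so the consequence has to be stated as conditional.

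Third, protocol Section 9.4.2 defines TEAEs as starting on or after the first dose, with no 28-day limit. Against that definition neither SFU window is complete, and the zero gap at day 28 holds only for the SAP definition. This stands, but it makes closing on day 21 no less of a loss.

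Last, the impact is small. That is correct and is reflected in the verdict.

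**Conclusion.** The inconsistency is real and in current text. For a patient seen on days 21 to 27, Table 7-1 and note ee together allow AE recording to close 1 to 7 days before the SAP's window ends; from day 28 the gap is zero. That the wording conflicts is certain. That events would actually be missed depends on a site scheduling early and on long-term follow-up not collecting them, and the documents settle neither.

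The likely effect on the single-arm, descriptive safety tables is small:

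- Serious related events count as TEAEs at any time (SAP Section 6.11.2) and must be reported if the investigator learns of them (Section 8.2.3.1).
- All deaths are listed (SAP Section 6.11.3).
- AEs already reported are followed at later contacts (Section 8.2.3.2).
- Each patient counts once per term, so a missed event changes a table only if it is a first occurrence, a higher grade or a closer relationship to treatment.

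The primary endpoint, ORR, is untouched. This is a minor correction worth making.

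**What to change.** Change the SFU column header in Table 7-1, note b and the parenthesis in Section 6.3.1 to 28 days (+7 days), matching Sections 3.3 and 7.5. The earliest permitted visit becomes day 28 and the gap to the SAP window becomes zero.

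If the sponsor prefers to keep the ±7-day flexibility, Sections 3.3 and 7.5 would have to be changed to match. Note ee should then say that AEs are recorded through the SFU visit or day 28 after the last dose, whichever is later.

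The preferred fix costs wording in three places. The Table 7-1 window narrows from 15 calendar days to 8, which Sections 3.3 and 7.5 already require, and no visit or procedure is added. Because amendments need IRB/IEC approval (Section 10.1) and about 40 institutions are planned (Section 3.7), it is best carried in the next amendment rather than issued alone.

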- All prior local treatments for CNS disease (e.g. surgery, whole brain radiation [WBRT], SRS), the start and stop dates for each prior local therapy, the specific lesions treated (if SRS and/or surgery), whether the patient developed intracranial progression after the last prior local treatment, and which lesions progressed since completion of the local therapy must be documented.
27. Clinically significant active cardiovascular disease or history of myocardial infarction within 6 months prior to planned start of selpercatinib or prolongation of the QT interval corrected for heart rate using Fridericia's formula (QTcF) > 470 msec. Correction of suspected drug-induced QTcF prolongation may be attempted at the investigator's discretion if clinically safe to do so.
 28. History of Human Immunodeficiency Virus (known HIV 1/2 antibodies positive); patients with unknown HIV status do not need to be tested.
 29. History of active hepatitis B (known positive hepatitis B surface antigen [HbsAg] and quantitative hepatitis B DNA greater than the upper limit of detection of the assay) or C (known positive hepatitis C antibody and quantitative hepatitis C RNA greater than the upper limit of detection of the assay); patients with unknown hepatitis B/hepatitis C status do not need to be tested.
 30. Active uncontrolled systemic bacterial, viral, or fungal infection or serious ongoing intercurrent illness, such as hypertension or diabetes, despite optimal treatment. Screening for chronic conditions is not required.
 31. Clinically significant active malabsorption syndrome or other condition likely to affect gastrointestinal absorption of the study drug.
 32. Uncontrolled symptomatic hyperthyroidism or hypothyroidism.
 33. Uncontrolled symptomatic hypercalcemia or hypocalcemia.
 34. Concurrent use of drugs known to prolong QTc (refer to [Appendix D](#) of the main protocol)
 35. Pregnancy or lactation. Breast-feeding should be interrupted when selpercatinib is started; breast-feeding can be resumed 3 months after discontinuation of selpercatinib.
 36. Active second malignancy other than minor treatment of indolent cancers with prior sponsor approval.

5 Enrollment Procedures

For all patients, a copy of the redacted Molecular Pathology Report, or other report(s) describing tumor *RET* (and/or other) alteration analysis must be submitted to the Sponsor or designee during Screening for review prior to patient enrollment.

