- k. Obtain a single pre-dose ECG during Screening and again on C1D1. If the C1D1 pre-dose QTcF > 470 msec (QTcF = QT (msec)/RR^{1/3}), where RR (msec) = $60 \times 1000/\text{BPM}$), the Sponsor should be notified prior to dosing to determine whether the patient remains eligible. On C1D8, C2D1 and thereafter, perform a single ECG at 2 hours (± 10 minutes) post-selpercatinib dosing. On C1D8 PK collection, an extra ECG should be timed prior to the PK sample being drawn. Dose patients in the visit to ensure accuracy of timing. If any ECG demonstrates QTcF 481-500 msec, perform an additional ECG at the same day, specific time judged by investigator. If any ECG demonstrates QTcF > 500 msec, repeat the ECG twice (triplicate in total) at the same day, specific time judged by investigator, and manually review to confirm accuracy. If QTcF > 500 msec is confirmed on 2/3 ECGs, hold selpercatinib and assess for alternative causes (concomitant medications, electrolyte abnormalities). Potassium should be > 4 mEq/L and $< \text{ULN}$ and magnesium and calcium should be within normal limits. selpercatinib may be resumed at one reduced dose level when QTcF has returned to baseline value, and with continued ECG monitoring as noted in the assessment schedule.
- l. Repeat only if EOT reading showed treatment-emergent abnormalities.
- m. For women of childbearing potential: Serum pregnancy test at Screening, serum or urine pregnancy test at Day 1 of every cycle (-2 days) (surgically sterilized females or those who have not experienced menses for at least 2 years are not required to be tested i.e., post-menopausal women who have not had menses within the last 12 months but have had menses within the last 24 months will be required to have a serum pregnancy test performed.). If screening testing is performed ≤ 7 days prior to C1D1, repeat testing does not need to occur on C1D1.
- n. Hemoglobin, hematocrit, RBC count, WBC count with differential (neutrophils [count and percent] and lymphocytes, monocytes, eosinophils, basophils [percent]), and platelet count). Patients found to have treatment-emergent hematologic toxicity of Grades 3 or 4 will be monitored at least weekly until resolution. If screening testing is performed ≤ 7 days prior to C1D1, repeat testing does not need to occur on C1D1.

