8.2 Safety Assessments

8.2.1 *Electrocardiograms*

ECG monitoring should be performed as outlined in the SoA (Table 7-1). The actions below should be taken if the triplicate average QTcF is greater than 500 msec.

- Manually review to confirm accuracy
- Assess for alternative causes (concomitant medications, electrolyte abnormalities, presence of pacemaker). Potassium should be ≥ 4 mEq/L and $<$ ULN and magnesium and calcium should be within normal limits.
- Institutional guidelines or SOC measures for management of QTcF interval >500 msec and/or associated arrhythmias should be initiated.
- Clinical chemistry should be assessed and if electrolytes are abnormal, they should be repeated as indicated.

If a patient experiences a QTcF interval >500 msec and if the investigator deems it in the best interest of the patient, the patient may continue treatment with study drug (with a dose reduction).

8.2.2 **Clinical Safety Laboratory Assessments**

- Investigator sites may use local laboratories to determine patient eligibility and treatment decisions.
- In addition, blood will be collected,
 - See [Appendix H](#) for the list of clinical laboratory tests to be performed and [Table 7-1](#) (Schedule of Activities) for the timing and frequency.
 - The investigator should review any clinically significant abnormal laboratory findings and assess relevance to patient care. If the laboratory findings are clinically significant, the investigator should document the findings as an adverse event in the case report form. The laboratory reports must be filed with the source documents. Clinically significant abnormal laboratory findings are based on investigator judgement.
- Regardless of whether or not central or local laboratory tests are used to determine patient care decisions, all laboratory tests with values considered clinically significantly abnormal during participation in the study or until completion of SFU should be repeated until the values return to normal or baseline or are no longer considered clinically significant by the investigator.
 - If such values do not return to normal/baseline within a period of time judged reasonable by the investigator, the etiology should be identified, and the sponsor notified.
 - All protocol-required laboratory assessments, as defined in [Appendix H](#), must be conducted in accordance with the laboratory manual and the SoA.

8.2.2.1 **Hepatic Safety Monitoring**

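### For QTcF above 500 msec, Table 7-1 note k requires a hold, while Section 8.2.1 uses a different trigger, names no hold and allows continued dosing at a reduced dose

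*Protocol*

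**What the plan says.** Three places in the protocol bear on a QTcF above 500 msec.

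- **Table 7-1, note k.** The note gives the heart-rate correction, which in the extracted text begins "QTcF = QT (msec)/RR^{1/3}), where RR (msec", and then the limits that apply to it. Any reading above 500 msec is repeated twice the same day, giving a triplicate, and reviewed by hand. Then: "If QTcF > 500 msec is confirmed on 2/3 ECGs, hold selpercatinib", with a search for other causes and an electrolyte check. On restart: "selpercatinib may be resumed at one reduced dose level when QTcF has returned to baseline value".
- **Section 8.2.1.** It opens with "ECG monitoring should be performed as outlined in the SoA" and then sets its own trigger: "The actions below should be taken if the triplicate average QTcF is greater than 500 msec". The listed actions are manual review, alternative causes, institutional or standard-of-care measures, and chemistry. It closes by saying that, for a patient with QTcF above 500 msec and if the investigator thinks it in the patient's best interest, "the patient may continue treatment with study drug (with a dose reduction". It mentions neither a hold nor a return to baseline.
- **Section 6.2.4.** It sends the reader to Section 8.2.1 for ECG dose modifications and does not mention note k. It adds that a patient above 500 msec despite two dose reductions may continue with approval from the sponsor's physician or scientist (CRP/CRS).

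**The concern.** A site facing a prolonged QTcF needs to know what triggers action, whether the drug stops, and when it may restart. The two texts differ on the first. On the other two, note k is explicit and Section 8.2.1 is silent or permissive. The dosing section points only to Section 8.2.1, so a site that follows the cross-reference could keep dosing a patient whom note k requires to be held.

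This is a safety matter for a drug with known QT prolongation. Section 1.5 reports it in 17.5% of LIBRETTO-001 patients, 4.0% at Grade 3-4. The statistical consequence is minor: differences between sites would show in the dose omissions, dose reductions and dose intensities that the SAP summarises (Section 6.11.1).

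**Working it through.** **Step 1: the rules side by side.**

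| Element | Table 7-1 note k | Section 8.2.1 |
|---|---|---|
| Trigger | At least 2 of 3 ECGs above 500 msec | Mean of the three above 500 msec |
| Drug | Hold | No hold named; may continue, reduced |
| Restart condition | QTcF back at baseline | None stated |
| Dose afterwards | One level lower | Reduced, number of levels not stated |
| Cited by Section 6.2.4 for ECG dose changes | No | Yes |

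**Step 2: does the action conflict arise when both triggers are met?** Take 510/510/510 msec. All three readings exceed 500, so note k is met. The mean is 510, so Section 8.2.1 is met. Note k says stop until baseline. Section 8.2.1, read alone, permits continuing at a reduced dose. This conflict needs no assumption about how QTcF varies.

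**Step 3: can the triggers separate?** Yes, in both directions.

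- 505/505/470: two of three exceed 500; mean = 1480/3 = 493.3. Note k only.
- 530/495/495: one of three exceeds 500; mean = 1520/3 = 506.7. Section 8.2.1 only.

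**Step 4: how many patients?** The documents give no rate for confirmed QTcF above 500 msec. As an assumed proxy, use the 4.0% Grade 3-4 rate from LIBRETTO-001. CTCAE grading is not reproduced in the protocol, and unconfirmed readings are not counted, so this is rough. With about 75 patients planned: 0.04 × 75 = 3.

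**Step 5: how often would the triggers alone disagree?** This needs the within-day correlation of QTcF and the patient's true mean, neither of which the documents give. Simulated triplicates of normal readings with equal pairwise correlation, kept when the first reading exceeds 500, give the following for a true mean of exactly 500:

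| Assumed correlation | Triggers disagree |
|---|---|
| 0 | 16.2% |
| 0.6 | 7.5% |
| 0.7 | 6.3% |
| 0.8 | 5.0% |

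About two thirds of these are note k only. With correlation 0.6 to 0.8, the rate is 9 to 13% if the true mean is 1 SD below 500 and about 2% if it is 1 SD above. Applying 5 to 13% to 3 patients gives 3 × 0.05 = 0.15 to 3 × 0.13 = 0.39 patients. These figures are illustrative only.

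**The case against.** The best case for the plan is that the texts complement each other. The opening bullets of Section 8 make adherence to the Schedule of Activities mandatory, and Section 8.2.1 defers to that schedule for ECG monitoring, so note k's hold binds every site. Nothing in Section 8.2.1 forbids a hold, and nothing in note k forbids the work-up in Section 8.2.1. Continuing with a dose reduction can be read as the stage after the hold, which would match note k's restart. Institutional measures may include a hold. Section 6.2.4 also interrupts dosing for Grade 3 or greater adverse events.

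Much of this stands. Note k is binding, and a careful site can often satisfy both sections. It does not settle the matter. The deferral in Section 8.2.1 covers monitoring; for action the section sets its own trigger and its own permission. The order of hold and reduction is an inference. Institutional practice varies by site. The Grade 3 rule depends on grading that the protocol does not reproduce, and it does not reconcile the triggers.

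Three stronger readings are tempting, and the documents do not support them.

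- **That the QTcF formula in note k is wrong by a factor of ten.** As it appears in the extracted text, RR is in msec, so QT 400 msec at 60 bpm gives 400/1000^(1/3) = 40.0 instead of 400. But the line has an unmatched closing bracket beside a superscript, so a term such as RR/1000 may have been lost in reading the PDF. Exclusion 27 names the Fridericia correction, and a value near 40 would be seen as absurd. At most, check the source page.
- **That the two-dose-reductions clause in Section 6.2.4 is a further conflict.** It is a special case added to a general rule.
- **That many patients would be handled differently.** Steps 4 and 5 do not support that.

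**Conclusion.** The inconsistency is real and rests on plain prose. For the same confirmed QTcF above 500 msec, note k requires a hold until baseline, while the section named for ECG dose changes uses another trigger, names no hold and allows dosing to continue at a reduced dose. The main defect is the action. The trigger mismatch is secondary and, on the assumptions above, would touch less than half a patient in expectation.

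The action conflict could concern about 3 of 75 patients if the LIBRETTO-001 Grade 3-4 rate is a fair proxy. That is few people, but it is a serious dosing decision spread over about 40 sites. No efficacy endpoint is affected. It is worth correcting because the correction is cheap and the text as it stands could lead a site to keep dosing when it should stop.

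**What to change.** Write one rule and print it in the same words in Section 8.2.1 and note k:

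- Hold selpercatinib if QTcF exceeds 500 msec on at least 2 of 3 ECGs, or if the triplicate average exceeds 500 msec.
- Treatment may continue only after that hold, one dose level lower, once QTcF has returned to baseline.

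Have Section 6.2.4 cite both places, and leave its two-dose-reductions clause as the special case it is. The potassium target can be aligned at the same time: note k asks for above 4 mEq/L, Section 8.2.1 for at least 4 mEq/L.

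Using either trigger keeps patterns such as 530/495/495 within the rule, which note k alone would miss. The price is a few more temporary holds. No extra ECGs are needed, because the triplicate is already required after any reading above 500 msec. The change alters dosing text, so it belongs in the next protocol amendment, with ethics committee approval under Section 10.1. The clinical choice of trigger remains the sponsor's.
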